4.10 Prior and Concomitant Therapy

Subjects will be randomized to either EndoRotor® or continued ablative therapy arms – no other treatments are allowed for study subjects. Endoscopic surveillance and biopsies every 3 months will be performed in both groups. Subjects with refractory Barrett's metaplasia after 3 failed radiofrequency ablations (RFA) are eligible for this study.

4.11 Informed Consent

Prior to the EndoRotor® procedure and enrollment in the ENDOROTOR study, written informed consent will be obtained in accordance with 21 CFR 50.20 and contain the information required by each of the eight basic elements of 21 CFR 50.25(a).

4.12 Inclusion Criteria

Candidates for this study must meet **ALL** of the following Inclusion criteria:

1. Subjects who are ≥ 30 and < 79 years of age; inclusive of males and females.
2. Subjects with a history of confirmed Barrett's esophagus with dysplasia (low-grade or high-grade) refractory to radiofrequency ablation 3 times.
3. Residual Barrett's length is ≥ 1 cm and ≤ 6 cm.
4. Histologic persistence of intestinal metaplasia (any non-squamous epithelial lesion) following treatment and failed eradication.
5. Following 3 failed RFA procedures with no confirmed evidence of EAC and having confirmed no endoscopic and histologic evidence of EAC at the time of therapy.
6. Subject capable of giving informed consent.
7. Subject has a reasonable expectation for prolonged survival (greater than 5 years).
8. Subject can tolerate repeated endoscopic procedures.
9. Absence of strictures that preclude the passage of the endoscope.
10. Subjects with the ability to understand the requirements of the study, who have provided written informed consent, and who are willing and able to return for the required follow-up assessments through 6 months or 9 months, as indicated.

4.13 Exclusion Criteria

Subjects will not be included in the study if **ANY** of the following exclusion criteria are met:

1. Subject unable to give informed consent.
2. Subject is unwilling to return for repeated endoscopies.
3. Subject having 3 failed RFA procedures and confirmed endoscopic and histologic evidence of EAC at time of therapy.
4. Residual Barrett's longer than 6 cm.
5. Subjects with nodular Barrett's Esophagus.
6. Subjects who are on aspirin or anticoagulant therapy who cannot stop it and have had bleeding problems during previous endoscopic treatments.
7. Esophageal varices.
8. Active esophagitis.
9. Esophageal stricture preventing passage of endoscope or catheter.
10. Any previous esophageal surgery, except fundoplication without complications.
11. Medically uncorrectable hypotension or hypertension.
12. Any condition that in the opinion of the investigator would create an unsafe clinical situation that would not allow the patient to safely undergo an endoscopic procedure (lack of medical clearance).
13. Pregnant or lactating women or women of childbearing potential who do not employ a reliable method of contraception as judged by the Investigator, and/or are not willing to use reliable contraception for the duration of study participation.
14. Patient has known severe psychiatric disorder, substance abuse, or other reason for being unable to follow trial follow-up instructions.
15. Patient has a known significant concomitant illness with a life expectancy of <1 year.
16. Patient is known to be currently enrolled in another investigational trial that could interfere with the endpoint analyses of this trial.

4.14 Study Withdrawal & Lost to Follow Up

Study participation is voluntary and subjects may withdraw their consent at any time. **ALL** enrolled subjects and their status in the study will be included in the study reports.

- **Treated and Study Criteria Not Met:** Subjects who are enrolled and treated, but who are later discovered to not meet all of the study criteria, will remain in the study and complete all of the study testing and follow-up requirements. A protocol deviation will be completed for study subjects who are found to be ineligible after enrollment. These subjects may be excluded from the Per Protocol analysis depending upon the nature of the protocol deviation.
- **Patient Withdrawal:** Participation in any clinical investigation is voluntary and a patient is allowed to discontinue their participation at any time. Subjects may withdraw at their own discretion with or without reason and without any impact on their continued medical care. If a patient voluntarily withdraws from the study, no additional medical data will be collected and the patient will not continue in the study.
- Subjects who withdraw from the study will not be replaced; however, if a patient withdraws their consent **BEFORE** being treated with the study device (before insertion of the catheter into the esophagus), and/or before the 9-month follow-up, he or she will not be included in the Per Protocol

- **Investigator Termination:** The site Investigator may terminate the patient's procedure if it is in the patient's best interest not to continue; however, the patient is not withdrawn from the study and will be included in the PP analysis.
- **Lost-to-Follow-up:** A patient who does not complete follow-up requirements and does not officially withdraw from the study is considered lost-to-follow-up. This does not apply to missed visits where the patient misses one of the follow-up contact time points, but completes the subsequent one. In order to consider a patient lost-to-follow-up, site personnel should make all reasonable efforts to locate and communicate with the patient. All attempts to contact the patient must be recorded in the study notes, including the date, time, and name of site personnel who have attempted to contact the patient.

5.0 STUDY PROCEDURES

5.1 Overview of Study Procedure and Flow of Patient Care

Refer to **Appendix 1** for a Schedule of Study Assessments.

5.1.1 Baseline Evaluation, not greater than 3 months prior to the Index Procedure

The following baseline evaluations will be assessed and recorded on all subjects who provide written informed consent:

- Demographic information and medical history including risk factors
 - PT/PTT within 2 days of the procedure
 - Pregnancy test within 1 day of the procedure
 - Cryotherapy treatments
 - Assessment against Inclusion/Exclusion criteria
- Medical clearance within 1 week of the procedure
- Biopsy-proven RFA-recalcitrant Barrett's Esophagus with low- or high-grade dysplasia – within the past 3 months.

5.1.2 Baseline Demographics and Relevant Medical History

The subject's demographic information and relevant medical history will be documented in the subject's source medical record and on the appropriate case report form (CRF). This will include the subject's:

- Age
- Gender
- Height
- Weight
- Race and Ethnicity Information
- Relevant medical history
- Physical Examination

5.2 Randomization Scheme

Randomization will be performed within 2 weeks of the procedure separately within each site using a 1:1 ratio

to EndoRotor® or continued ablative therapy, with blocking to be specified in separate randomization documentation. A total of 110 sealed envelopes, 55 of which contain a designation of "EndoRotor® resection" and the other 55 with the designation "Continued Ablative Therapy" will be produced. The investigator will have access to the envelopes and will designate one other person at each site to be in charge of distributing the envelopes during recruitment. The envelopes will be stored in a locked cabinet within a secure locked office at the site. If patients are lost to follow-up, additional envelopes will be provided to the site.

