4.8 Subject Recruitment

The subjects will be recruited from the clinical practices of the investigators. Due to the number of recalcitrant Barrett's subjects they follow and are referred each month, there may not be a need to advertise. These centers are major referral centers for advanced cases such as refractory Barrett's esophagus. Subjects

who have failed 3 RFA treatments will be told of the study and asked if they would be interested in participating.

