5.5 Index Procedure

5.5.1 Eligibility

The Investigator will verify informed consent and confirm the subject meets all inclusion / exclusion criteria. The Investigator, or designee, will record in the subject's source medical record that informed consent was verified, and all inclusion / exclusion criteria were confirmed prior to the index study procedure.

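### Allocation concealment is not secured: the investigator who recruits and confirms eligibility also has access to the site-held envelopes and appoints the person who hands them out

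*Combined protocol and SAP*

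**What the plan says.** Section 5.2 sets out the whole allocation procedure.

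- Assignment is by site: "Randomization will be performed within 2 weeks of the procedure separately within each site using a 1:1 ratio".
- The block size is not given: "with blocking to be specified in separate randomization documentation".
- The vehicle is paper: "A total of 110 sealed envelopes, 55 of which contain a designation of" EndoRotor and the other 55 control.
- On custody: "The envelopes will be stored in a locked cabinet within a secure locked office at the site".
- On access: "The investigator will have access to the envelopes". The investigator also "will designate one other person at each site to be in charge of distributing the envelopes during recruitment".

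Other sections place the same role at each decision around assignment. Section 4.8 says "The subjects will be recruited from the clinical practices of the investigators". Section 5.5.1 says "The Investigator will verify informed consent and confirm the subject meets all inclusion / exclusion criteria". Section 5.5.3 leaves the choice between RFA and cryotherapy in the control arm to the investigator.

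Section 5.2 does not call for opaque, sequentially numbered or tamper-evident envelopes, for a record made before opening, or for a distributor who stands outside screening and treatment. It names no central assignment. The only blinding described is of specimen labels (5.8.1).

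**The concern.** Concealment means that whoever decides whether and when a subject enters cannot learn the next assignment first. Here the protocol expressly grants envelope access to the role that makes that decision. This is a stated rule, not a gap left by silence.

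If the next assignment is known or suspected, a subject who looks hard to clear can be delayed, discouraged or judged ineligible when one arm is due, and entered when the other is. The arms then differ in prognosis before treatment, and both the non-inferiority and the superiority comparison inherit that difference. The trial is called pivotal in Section 4.5 and its effectiveness claims rest on the randomized comparison. With a resection device set against RFA or cryotherapy, site staff will see each past assignment, so concealment of the next one is the main protection left against selection.

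**Working it through.** **1. Who can do what.**

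| Step | Role | Section |
|---|---|---|
| Recruits from own practice | Investigator | 4.8 |
| Has access to envelopes | Investigator | 5.2 |
| Appoints the distributor | Investigator | 5.2 |
| Distributes envelopes | One other person; independence not required | 5.2 |
| Confirms criteria before the index procedure | Investigator | 5.5.1 |
| Chooses the control device | Investigator | 5.5.3 |

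No other section withdraws the access. Section 5.2 allows randomization up to 2 weeks before the procedure, and Section 5.5.2 makes a subject who fails criteria at the index procedure an untreated screen failure. So an eligibility judgment can also fall after the assignment is known.

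**2. The plan's own figure.** The documents quantify nothing about concealment. The nearest figure is the superiority power in Section 7.3: 91.6% with 55 per arm, 80% against 50%, two-sided 0.05. With pooled variance, the mean rate is 0.65, the null SE is √(2×0.65×0.35/55) = 0.0910 and the alternative SE is √((0.16+0.25)/55) = 0.0863. Power is Φ((0.30 − 1.96×0.0910)/0.0863) = Φ(1.41) = 92.1%, close to the stated value. The 55 per arm and the 50% control rate are therefore a sound base for the illustration. The fix alters neither N nor power.

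**3. Guessing without opening anything.** The block size is assumed, because the documents do not give it. The guesser knows past assignments at the site and always names the arm with more places left in the block. In a block of 4, the chance of being right at each position is:

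- first: 1/2
- second: 2/3
- third: (1/3)×1 + (2/3)×(1/2) = 2/3
- fourth: 1

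The mean is (0.500 + 0.667 + 0.667 + 1)/4 = 70.8%, and 1/3 of assignments are certain. The same enumeration for a block of 6 gives 68.3%, with 1/4 certain.

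**4. Effect of a prognostic shift on error.** The assumptions are 55 per arm, control success 50%, no true difference, and selection that raises the EndoRotor arm's success rate by s. The unadjusted unpooled statistic is z = (p̂E − p̂C)/√(p̂E(1−p̂E)/55 + p̂C(1−p̂C)/55). The error is the exact binomial probability that z > 1.96.

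| s (points) | Unpooled z | Pooled z | Fisher's exact, two-sided 0.05 |
|---|---|---|---|
| 0 | 2.4% | 2.3% | 1.4% |
| 5 | 7.4% | 7.0% | 4.7% |
| 10 | 18.4% | 17.3% | 12.7% |

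For non-inferiority, take a true difference of −10 points, control at 50%, and the normal approximation 1 − Φ(1.96 − s/SE). With s = 5 points, SE = √((0.25+0.2475)/55) = 0.0951 and the error is 7.6%. With s = 10 points, SE = √(0.50/55) = 0.0953 and the error is 18.1%. With no shift it is 2.5%.

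The values of s are not taken from the documents. They must be read as what remains after the planned covariate adjustment.

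**The case against.** Section 5.2 does contain safeguards: the envelopes are sealed, locked in a cabinet inside a locked office, and distributed by someone other than the investigator. A reader might infer from the access sentence that allocation is not concealed at all, that the investigator holds the key, or that the next assignment is fully predictable. The documents support none of these. They say access without saying who holds a key or whether access extends to unopened envelopes. Full predictability would require someone to open or read through a sealed envelope, or to know the order.

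The planned logistic model (7.4) adjusts for age, dysplasia grade, lesion length and disease duration, so steering by length would be partly corrected. The primary population is all randomized subjects, analyzed as randomized (7.2). Sites keep a screening and enrollment log (8.5), notify enrollment or treatment within 48 hours (8.3, 8.7) and are monitored (9.5).

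All of this stands, and it limits the claim. It does not remove it. Sealing and locking protect little against a person who is granted access, and the distributor is that person's appointee. The log and monitoring may help reveal skipped or delayed subjects afterward, but they do not prevent it. Intention-to-treat analysis cannot undo selection that happens before assignment. Circumferential extent, scarring and the operator's sense of difficulty are not in the model.

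**Conclusion.** The point holds as a weakness in procedure: concealment is not secured, because the protocol gives envelope access to the role that controls entry and does not require an independent distributor. It should be changed before the first subject is randomized, since selection bias cannot be reliably removed later.

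No bias is demonstrated. A reader might take the 7.4% and 18.4% as a forecast of the trial's error rate. They show sensitivity only, and rest on assumed residual shifts of 5 and 10 points, a 50% success rate and an unadjusted unpooled z-test in place of the planned adjusted model. Fisher's exact test gives lower values for the same shifts. The 71% and 68% rest on assumed block sizes. That treatment is unmasked is an inference from the nature of the two arms and from the absence of any blinding beyond specimen labels; the documents do not use the term open-label.

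**What to change.** In Section 5.2:

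1. Delete the investigator's access to the envelopes.
2. Require that the second person already planned for each site takes no part in screening or treatment, and make that person sole custodian.
3. Specify sequentially numbered, opaque, tamper-evident envelopes, used strictly in order.
4. Allow an envelope to be opened only after the subject's ID, the date and confirmed eligibility have been written on it and entered in a log.
5. State that block sizes are withheld from site staff. Without this, the guessing shown above remains possible even with perfect custody.

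The cost is mainly protocol wording and an envelope specification. Each site must also assign the custodian role to an existing staff member outside screening and treatment. The documents do not show that the person now foreseen meets that condition, so some sites may have to choose someone else.

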5.3 Laboratory Tests

Results from the subject's following laboratory tests will be documented in the subject's source medical record and on the appropriate CRF:

- Urine pregnancy test if female of child-bearing age within 1 day of procedure

5.4 Pain Assessment

Subjects will be asked to describe their pain level using a visual analog pain scale just before the index procedure. Subjects will be asked to describe their pain level using the same pain scale prior to discharge and will be compared to the pre-procedure assessment. Pain assessment will be repeated at each follow up visit. The assessments will be recorded on the case report forms.

5.5 Index Procedure

5.5.1 Eligibility

The Investigator will verify informed consent and confirm the subject meets all inclusion / exclusion criteria. The Investigator, or designee, will record in the subject's source medical record that informed consent was verified, and all inclusion / exclusion criteria were confirmed prior to the index study procedure.

5.5.2 Screen Failures

Enrolled subjects failing to meet inclusion / exclusion criteria at the time of index procedure will not be treated with the EndoRotor® device or the control device and; therefore, are classified as screen failures. Any baseline study data captured in the CRFs will be collected. Only subjects in whom the EndoRotor® catheter or ablative therapy catheter enters the esophagus will be followed and study data analyzed [per protocol set (PPS)].

5.5.3 Index Procedure

Once enrolled, each patient will be randomized into either the EndoRotor® mucosal resection arm or the control ablation arm. Randomization will occur within 2 weeks of the procedure. The investigators shall follow the technique described by the manufacturer's instructions as provided in the Instructions for Use.

Endoscopic treatment of the esophagus will be performed within 6 weeks of enrollment with outpatient video documentation of the residual Barrett's changes during upper endoscopy.

EndoRotor® Arm: At this point, the EndoRotor® will be set-up and used to resect the mucosa and submucosa to remove all gross visible disease. Lesions will be "lifted" using saline solution with dye such as Indigo carmine or Methylene Blue. Indelible ink (such as SPOT) will be injected into the region of the resection to identify the site after resection. If the lesion is circumferential, the endoscopist shall resect no greater than 270 degrees of the radial circumference of the esophagus to avoid stricture formation. The resection is taken down to the muscularis propria layer to ensure all of the mucosa and submucosa is removed in the area of persistence.

The EndoRotor® is set to either High Speed (1700 RPM) or low speed (1000 RPM) based on user preference and the vacuum is set to between 250 mmHg and 350 mmHg of negative pressure. The endoscopist will start the EndoRotor® motor using the left foot pedal, and will activate the cutting by depressing and holding the

right pedal down for as long as he wants to resect tissue. The procedure is repeated until the entire gross visible lesion has been removed down to the muscularis propria without entering the muscle layer. The specimen can be sent to Pathology by removing the filter in the specimen trap. A new filter is placed in the specimen trap allowing multiple lesions to be treated and analyzed histopathologically.

Continued Ablative Therapy Arm: The investigator shall exercise standard of care for continued ablative therapies namely RFA (HALO 90/60) and/or cleared cryotherapy devices. These will constitute two control devices. The investigator will choose the system in this arm. Operation of the each system will be done according to the manufacturer's instructions for use. The type of system used will be indicated on the case report forms.

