4.9 Subject Screening

Following 3 failed radiofrequency ablations where study eligibility is confirmed, the patient will receive the EndoRotor® device. The patient will be enrolled upon insertion of the catheter into the esophagus. Screening shall include:

- Pregnancy test – within 1 day of the procedure.
- PT/PTT – within 2 days of the procedure.
- Medical clearance within 1 week of the procedure.
- Having confirmed no evidence of EAC during 3 RFA failures and no endoscopic and histologic evidence of EAC at the time of treatment.
- Biopsy-proven RFA-recalcitrant Barrett's Esophagus with low- or high-grade dysplasia – within the past 3 months.
- Ideally, subjects should not be on aspirin or Clopidogrel therapy, but if they are, there should be no history of bleeding during endoscopic treatments.

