APPENDIX 1 – SCHEDULE OF STUDY ASSESSMENTS

A schedule of study assessments is provided below.

| | Baseline (≤14 days) | Index Procedure (Day 0) ³ | Discharge | 3 Months (±14 days) | 6 Months (±14 days) ³ | 9 Months (±14 days) ⁴ |
|---|---------------------------|--|-----------|---------------------------|--|--|
| Confirm Eligibility | X | X | | | | |
| Informed Consent | X | | | | | |
| Randomization | X | | | | | |
| Demographics | X | | | | | |
| Medical History | X | | | | | |
| Physical Examination | X | | | | | |
| Pregnancy Test ¹ | X | | | | | |
| EndoRotor® or Continued Ablative Therapy Procedure | | X | | X | X ⁴ | X ⁵ |
| Surveillance Biopsies | | X | | X | X ⁴ | X ⁵ |
| Adverse Event Assessment | | X | X | X | X ⁴ | X ⁵ |
| Analog Pain Scale ² | | X | X | X | X | X |

¹ Urine pregnancy test for female of child bearing potential within 1 day of procedure.

² Pain assessment should be completed just prior to each endoscopic procedure and at discharge.

³ The index procedure must be done within 6 weeks of enrollment with outpatient video documentation of the residual Barrett's changes during upper endoscopy.

⁴ The exam at day 6 months is not required if there is no presence of intestinal metaplasia (Barrett's) on biopsies from the preceding exam.

⁵ The exam at day 9 months is not required if there is no presence of intestinal metaplasia (Barrett's) on biopsies from the preceding exam. See Section 5.7 Subject Follow-up.

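### Randomization may precede the final eligibility check by up to 2 weeks, and randomized subjects who fail that check are neither treated nor followed, although the primary ITT population is everyone randomized

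*Combined protocol and SAP*

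**What the plan says.** **Timing of allocation.** Section 5.2: "Randomization will be performed within 2 weeks of the procedure separately within each site using a 1:1 ratio". Section 5.5.3 repeats the 2-week window: "Randomization will occur within 2 weeks of the procedure". Appendix 1 marks randomization in the Baseline column (at most 14 days) and not under Day 0.

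**Timing of eligibility.** In Appendix 1 the eligibility row reads "Confirm Eligibility | X | X", that is, at baseline and again at the index procedure. Section 4.9 also asks for "Medical clearance within 1 week of the procedure", and the pregnancy test is due within 1 day. Inclusion criterion 5 (section 4.12) requires "having confirmed no endoscopic and histologic evidence of EAC at the time of therapy". Exclusion 12 (section 4.13) rests on the investigator's opinion.

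**What happens on failure.** Section 5.5.2: "Enrolled subjects failing to meet inclusion / exclusion criteria at the time of index procedure will not be treated with the EndoRotor® device". The sentence extends to the control device and classes these subjects as screen failures. Their baseline data are kept. Follow-up and analysis are confined to subjects whose esophagus a study or control catheter has entered, with a tag to the per-protocol set.

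**Who is analyzed.** Section 7.2 makes ITT primary, meaning all randomized subjects as randomized, with missing outcomes imputed. The Protocol Summary names per protocol as the primary analysis.

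**When a subject is enrolled.** Section 4.9: "The patient will be enrolled upon insertion of the catheter into the esophagus". Section 5.5.2 calls subjects enrolled before any catheter is used. Section 5.5.3 randomizes after enrollment, and both 5.5.3 and Appendix 1 allow 6 weeks from enrollment to the procedure.

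**The concern.** Randomization protects the comparison only if nobody is removed afterwards for reasons that could depend on the arm. Here the last eligibility decision can be made with the allocation known. The two treatments are visibly different, the investigator has access to the envelopes (5.2) and chooses the control system (5.5.3). Some of the criteria open at that point involve judgment, such as medical clearance, the endoscopic findings and exclusion 12.

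A subject removed then has no follow-up, so the primary ITT analysis has no outcome for that subject. If removals differ by arm and are related to prognosis, the estimated difference in complete removal is biased, and that difference serves both the non-inferiority and the superiority test. The conflicting definitions of enrollment add a reporting problem. Section 4.14 promises to account for all enrolled subjects, and whether a dropped subject is one of them depends on which section is read.

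**Working it through.** **1. The plan's own size and power.** 120 − 10 = 110 evaluable, 55 per arm (4.5, 7.3). For 80% against 50% at two-sided 0.05 with pooled variance:

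z = [0.30 − 1.96 × √(2 × 0.65 × 0.35 / 55)] / √[(0.16 + 0.25) / 55] = (0.30 − 0.178) / 0.0863 = 1.41, so power is 92.1%. Section 7.3 states 91.6%, which this reproduces closely.

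The allowance of 10 is for loss to follow-up only. Further loss unrelated to outcome lowers superiority power to 89.4% at 50 per arm and 85.2% at 44 per arm; non-inferiority power stays at 98.5% or more. Power is therefore a minor matter here, and bias is the main one.

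**2. Order of events the plan permits.**

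| Step | Timing | Source |
|---|---|---|
| First eligibility check | Baseline | Appendix 1 |
| Randomization | Up to 14 days before Day 0 | 5.2, 5.5.3, Appendix 1 |
| Medical clearance | Within 1 week | 4.9 |
| Pregnancy test | Within 1 day | 4.9 |
| Second eligibility check | Day 0 | 5.5.1, Appendix 1 |
| Failure: untreated, not followed | Day 0 | 5.5.2 |

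Section 5.5.1 requires confirmation before the index procedure. It does not require it before randomization.

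**3. Size of the possible bias.** Assumptions, none taken from trial data: 60 randomized per arm (120 at 1:1); true response 50% in both arms (50% is the control rate in 7.3); a fraction d of the EndoRotor arm is dropped on Day 0, all would-be failures; none dropped from control.

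- Dropped subjects excluded: EndoRotor rate = 0.50 / (1 − d).
- Dropped subjects kept in ITT and imputed under 7.5: the listed predictors are site, age, dysplasia grade, lesion length and disease duration, without arm. If these are uninformative, imputation draws from the pooled retained rate, 1 / (2 − d), so the EndoRotor rate = 0.50 + d / (2 − d).
- Worst-case analysis of 7.5 (missing EndoRotor counted as failure): 0.50 / (1 − d) × (1 − d) = 0.50, no advantage.

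| d | Dropped of 60 | Excluded: rate, advantage | Imputed: rate, advantage |
|---|---|---|---|
| 5% | 3 | 52.6%, 2.6 points | 52.6%, 2.6 points |
| 10% | 6 | 55.6%, 5.6 points | 55.3%, 5.3 points |
| 15% | 9 | 58.8%, 8.8 points | 58.1%, 8.1 points |

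Adding arm to the imputation model would not cure this. In this scenario imputing within arm returns 0.50 / (1 − d), the excluded figure. The cause is the absent outcome.

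**4. Effect on error rates, exclusion case.** With m = 60(1 − d) retained EndoRotor subjects, 60 controls and a pooled-variance test, the chance of falsely declaring EndoRotor superior is 4.7%, 8.5% and 15.0% for d = 5%, 10% and 15%, against a nominal 2.5%. For non-inferiority at a true 10-point deficit (40% against 50%), the false-positive rate is 4.2%, 6.9% and 11.2%, against 2.5%.

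**The case against.** The strongest reply is that the plan already has safeguards. Section 7.2 keeps every randomized subject in the primary denominator. The restriction in 5.5.2 carries a per-protocol tag and can be read as leaving ITT alone. Section 7.5 adds best-case, worst-case and tipping-point analyses, and the worst case removes the whole advantage in the illustration. Disposition is summarized (7.8.4), and the DMC sees ineligibility and dropouts overall and by site (10.2).

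Much of this stands. A reader might infer that a dropped subject's outcome can only be imputed from those kept; the worst-case and tipping-point analyses show otherwise. But they are sensitivity analyses, and they work only if these subjects stay in the dataset, which 5.5.2 leaves in doubt. Whatever the tag covers, 5.5.2 still denies follow-up, and the DMC list does not call for ineligibility by arm.

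It is also fair that the Day 0 check repeats a baseline check, that the windows are outer limits which permit the problematic order without requiring it, and that pregnancy is objective. PT/PTT is a screening test but not an inclusion or exclusion criterion, so it should not be counted among the late eligibility decisions. Of the endoscopic criteria, only those on EAC are worded as applying at the time of therapy.

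A reader might further infer that dropped subjects are not counted as enrolled. That follows only from 4.9; sections 5.5.2 and 5.5.3 treat them as enrolled. The supportable statement is that the definitions conflict.

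**Conclusion.** The point holds as a design weakness that should be corrected. The plan lets allocation precede the final eligibility decision by up to 14 days, leaves that decision to investigators who can know the arm, and gives no follow-up to randomized subjects who fail it. That is inconsistent with a primary population of all randomized subjects.

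The size is unknown, because the documents give no drop rate. The range of 2.6 to 8.8 points (excluded) or about 2.6 to 8.1 points (imputed under 7.5) is an extreme case. It assumes that 5% to 15% of one arm is dropped, none of the other, and that every dropped subject would have failed. The upper figure also takes these subjects out of the denominator, contrary to 7.2. It would be wrong to set 8.8 points against the 10-point margin as if it were an expected bias, or to infer that investigators would select in this way; nothing in the documents shows that. If dropping is unrelated to arm and outcome, the bias is zero and only a modest loss of power remains.

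**What to change.** 1. **Sections 5.2, 5.5.3 and Appendix 1.** Open the envelope only after final eligibility has been confirmed, as close to the index treatment as practical and before any study device is introduced. Move the randomization mark in Appendix 1 to match.
2. **Section 5.5.2.** Restrict screen failure to subjects not yet randomized. Replace the last sentence so that every randomized subject, treated or not, is followed and kept in ITT, and report post-randomization exclusions by arm and reason. This is needed even with item 1, because an endoscopy on the day of treatment cannot supply new histology and some ineligibility may still emerge after allocation.
3. **Sections 4.9, 5.5.2, 5.5.3 and Appendix 1.** Use one definition of enrollment. Align with it the event from which the 6-week limit runs, the start of adverse event recording (5.6 and 10.5) and the enrollment notifications (8.3 and 8.7).
4. **Protocol Summary and section 5.5.2.** Reconcile the stated primary population with section 7.2.

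The cost is mainly wording and one moved mark in the schedule. Both device systems must be available on the procedure day, and any randomized but untreated subjects need follow-up. The planned 55 evaluable per arm, and the power that goes with it, are unchanged.
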